4.2 Exclusion Criteria

Patients who meet any of the following criteria will be excluded from participation in the study:

- 1. Resting trough-cuff seated SBP ≥ 180 or < 140 mmHg, based on the mean of at least 2 current consecutive clinic blood pressure readings at Screening and the end of the placebo run-in period (Visit 3);
- 2. Serum potassium > 4.8 mmol/L;
- 3. Compliance with medications (including both open-label placebo and current antihypertensive medications) < 80% or > 120% during the run-in period (assessed at Visit 3);
- 4. Currently on an MRA (eg, spironolactone or eplerenone) other than KBP-5074, or received any MRAs during the last 3 months prior to Screening, or currently on any potassium supplements;
- 5. Chronic or intermittent use of a potassium binder for the treatment of hyperkalemia from 3 months prior to Screening until the end of study assessments, including but not limited to calcium polystyrene sulfonates (eg, sorbisterit, calcium resonium), sodium polystyrene sulfonates (eg, kayexalate, anti-kalium sodium), and patiromer (eg, Veltassa[™]) and sodium zirconium cyclosilicate (eg, Lokelma[™]);
- 6. Have routinely or chronically used or required potassium-sparing diuretics (eg, amiloride, triamterene) within 3 months prior to Screening until the end of study assessments;
- 7. History of known/suspected contraindications, allergy, or intolerance to MRAs (eg, spironolactone, eplerenone) or has a known hypersensitivity to KBP-5074, other MRAs, or related compounds;
- 8. Clinically significant hyperkalemia while on an angiotensin converting enzyme inhibitor, angiotensin receptor blocker, direct renin inhibitor, and/or MRA, requiring down-titration or discontinuation of above medication, or hospitalization for hyperkalemia within 3 months prior to Screening, or hyperkalemia > 5.6 mmol/L during the 2 weeks prior to Screening;
- 9. History/diagnosis of renal artery stenosis or history/diagnosis of renovascular hypertension;
- 10. Currently receiving HD, or peritoneal dialysis within 3 months prior to Screening, and those patients with an episode of acute kidney injury within 3 months of Screening;

- 11. History of a renal transplant, or impending renal transplant;
- 12. Acute decompensated heart failure including exacerbation of chronic heart failure manifested by signs and symptoms that may require hospitalization and/or intravenous diuretic therapy (New York Heart Association Class III to IV) within 3 months prior to Screening, or presence of hemodynamically significant valve diseases and/or other hemodynamically significant obstructive lesions of left ventricular outflow tract;
- 13. Major cardiac, cerebral, and/or carotid artery diseases, including but not limited to acute coronary syndrome, myocardial infarction, stroke, and/or transient ischemic attack; major cardiovascular or percutaneous procedures including cardiac ablation, coronary revascularization, and carotid angioplasty within 6 months prior to Screening; OR
 - Cardiovascular conditions likely to require surgical or percutaneous intervention within 6 months from Screening;
- 14. History of clinically significant arrhythmia, including but not limited to any of the following:
 - Symptomatic bradycardia and/or symptomatic ventricular arrhythmia within 3 months prior to Screening;
 - o Second- or third-degree heart block; or
 - New onset or untreated atrial fibrillation; Note: Patients with stable (6 months) asymptomatic rate controlled atrial fibrillation on appropriate therapy, which may include anticoagulation, are permitted.
- 15. QT interval corrected using Fridericia's formula (QTcF) > 450 ms for males or > 470 ms for females at Screening or Day 1; QTcF should be the average of the required triplicate set of ECGs at each timepoint;
- 16. History of prolonged QT interval;
- 17. History or family history of sudden cardiac death or long QT syndrome;
- 18. History of cardiac transplant, on a heart transplant list, or has a left ventricular assistance device;
- 19. History of clinically significant acute or chronic hepatitis (including infectious, metabolic, autoimmune, genetic, ischemic, or other forms), hepatocirrhosis, or hepatic tumors;
- 20. History of gastrointestinal surgery that might affect absorption/oral bioavailability of oral antihypertensive therapies including KBP-5074;
- 21. Clinically significant abnormal liver function test at Screening or the end of the run-in period (Visit 3), defined as aspartate aminotransferase or alanine aminotransferase > 3 × the upper limit of normal (ULN) or total bilirubin > 2 × ULN;
 - Note: Patients with total bilirubin > 2 × ULN and history of Gilbert's syndrome may be included.
- 22. Positive blood screen for human immunodeficiency virus (HIV), hepatitis B surface antigen (HbsAg), or hepatitis C virus (HCV) antibody;
- 23. History of malignancy in the past 5 years, with the exception of basal or resected cutaneous squamous cell carcinoma of the skin or carcinoma in situ, prostate cancer in situ with a normal

- prostate-specific antigen post treatment, cervical carcinoma in situ, gastric cancer in situ, colon cancer in situ adequately treated with no progression over the past 2 years;
- 24. History of prescription drug abuse, illicit drug use, or alcohol abuse according to medical history within 6 months prior to Screening;
- 25. A positive drug screen test (excluding a positive result secondary to a prescribed medication from a physician, or tetrahydrocannabinol) at Screening or the end of the run-in period (Visit 3);
- 26. Female patients who are known to be pregnant or breastfeeding;
- 27. Previously enrolled in any KBP-5074 study;
- 28. Receipt of any other investigational product within 30 days or 5 half-lives (whichever is longer) prior to Screening;
- 29. Use of any nutrients known to modulate cytochrome P450 (CYP)3A activity (based on the KBP-5074 metabolic pathway) or any strong or moderate inhibitors or inducers of CYP3A4, starting from 14 days prior to the first dose of study drug at Day 1 until the end of study assessments, including but not limited to the following: inhibitors, such as ketoconazole, miconazole, itraconazole, fluconazole, atazanavir, erythromycin, clarithromycin, ranitidine, and cimetidine, and inducers, such as rifampicin, rifabutin, glucocorticoids, carbamazepine, phenytoin, phenobarbital, and St. John's wort;
- 30. Has donated or lost a significant volume (> 500 mL) of blood or plasma within 30 days prior to Screening;
- 31. An employee or family member of the Investigator or study site personnel;
- 32. Unlikely to comply with the protocol requirements, instructions, and/or study-related restrictions (eg, uncooperative attitude, unavailable for follow up call, and/or improbability of completing the clinical study); and
- 33. History of any other prior or concomitant clinical condition or acute and/or unstable systemic disease not listed above that, in the opinion of the Investigator, compromises patient inclusion, such as a history or presence of clinically decompensated or unstable cardiovascular, pulmonary, hepatic, gallbladder or biliary tract, hematologic, gastrointestinal, endocrine, immunologic, dermatologic, neurologic, or psychiatric disease, or concomitant morbidity of such severity that the patient is likely to die within 1 year from Screening.

4.3 Withdrawal Criteria

Participation of a patient in this clinical study may be discontinued for any of the following reasons:

- The patient withdraws consent or requests discontinuation from the study for any reason;
- Significant protocol violation, including major protocol violations, such as taking prohibited medication or inability to comply with protocol procedure;

- Any clinically significant adverse event, severe laboratory abnormality, intercurrent illness, or other medical condition that indicates to the Investigator that continued participation is not in the best interest of the patient, including:
 - Hypertensive Emergency;
 - Hyperkalemia defined in Table 1; or
 - Sustained increase in serum creatinine defined as an increase > 50% in serum creatinine from baseline and confirmed by a repeated test (see Section 8.13);
- Pregnancy;
- Termination of the study by the Sponsor or regulatory authority; or
- Lost to follow-up.

If a patient withdraws prematurely from the study due to the above criteria or any other reason, study staff should make every effort to complete the full panel of assessments scheduled for the Early Termination Visit (see Section 6.6). The reason for patient withdrawal must be documented in the electronic Case Report Form (eCRF).

In the case of patients lost to follow-up, attempts to contact the patient must be made and documented in the patient's medical records.

Withdrawn patients will not be replaced.

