4 SELECTION AND WITHDRAWAL OF PATIENTS

4.1 Inclusion Criteria

Patients who meet all of the following criteria will be eligible to participate in the study:

- 1. Male or female, between 18 and 85 years of age, inclusive. The lower age limit may be higher if it is legally required in the participating country;
- 2. Body mass index between 19 and 45 kg/m², inclusive;
- 3. Stage 3B/4 CKD (defined as eGFR ≥ 15 and ≤ 44 mL/min/1.73 m², based on the isotope dilution mass spectrometry traceable MDRD equation version 4, according to central laboratory results at Screening [single retest is allowed]);
- 4. Uncontrolled hypertension (Grade 1 to 2 systolic hypertension ESC/ESH), defined as:
 - Resting trough-cuff seated SBP ≥ 140 and ≤ 179 mmHg based on the mean of at least 2 current consecutive clinic blood pressure readings at Screening and at the end of the placebo run-in period (Visit 3); AND
 - Currently on 2 or more antihypertensive medications, which have been titrated upward as tolerated to recommended hypertension target doses (such as diuretics [except for potassium-sparing diuretics], renin-angiotensin system blockers, and/or calcium channel blockers. One of the antihypertensive medications must be high ceiling diuretic (loop or thiazide-like), unless there is a documented intolerance or contraindication to diuretic therapy. The doses of the antihypertensive medications should be stable without any dose adjustment during the 30 days prior to randomization; OR
 - o Patients with uncontrolled hypertension and moderate-to-severe CKD with documented history of intolerance to multiple antihypertensive medications on fewer than 2 antihypertensive medications;
- 5. Serum potassium ≤ 4.8 mmol/L at both Screening and the end of the placebo run-in period. A single retest is allowed to exclude laboratory error or hemolyzed samples;
- 6. Women of childbearing potential (WOCBP) must agree to use 2 medically accepted, effective methods of birth control during the study and for 90 days after the end of the study. Adequate methods of contraception are defined as those that result in a low failure rate (< 1% per year) when used consistently and correctly. Such methods include the use of oral contraceptives, other hormonal contraceptives (vaginal products, skin patches, or implanted or injectable products), or mechanical products (such as an intrauterine diaphragm, condoms, or spermicides);

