5 STUDY TREATMENTS

5.1 Treatment Groups

After completion of the screening period and qualifying Screening Visit, patients who meet all eligibility criteria (except those criteria scheduled to be assessed after the Screening Visit) will enter a 2-week run-in period. During this time, all patients will be given open-label placebo.

At the Day 1 Visit (scheduled within 4 ± 2 days after the end of the run-in period [Visit 3]), eligible patients will be randomized by Interactive Response Technology (IRT) in a 1:1:1 ratio to the following treatment groups:

- KBP-5074 0.25 mg QD orally,
- KBP-5074 0.5 mg QD orally, or
- Placebo QD orally

The duration of the double-blind treatment period will be 84 days. Patients will remain on their stable antihypertensive medication (ie, no change in antihypertensive medication) throughout the entire study (including both the run-in and treatment periods). The dose of diuretic may be adjusted based on developing or resolved edema, weight gain or loss, or pulmonary congestion.

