6.4.2 Day 1 (Visit 4) \pm 2 Days

This visit is to be scheduled within 4 ± 2 days after the end of the run-in period (Visit 3).

The following procedures will be performed at Visit 4:

- Assess eligibility: Patients must have uncontrolled hypertension, defined as resting trough-cuff seated SBP ≥ 140 and ≤ 179 mmHg, based on the mean of at least 2 current consecutive blood pressure readings in the clinic. Prior to randomization, all patients are to have a serum potassium ≤ 4.8 mmol/L at both Screening and the end of the placebo run-in period; and a mean (Visit 1 and Visit 3) eGFR ≥ 15 and ≤ 44 mL/min/1.73 m².
- Record weight;
- Perform physical examination (pre-dose);
- Perform 12-lead ECG in triplicate (patients should be resting in a supine position for at least 10 minutes prior to assessment);
- Obtain vital signs, including pulse rate, respiratory rate, and oral temperature;
- Obtain blood pressure prior to study drug administration;
 - O Blood pressures are to be obtained according to the AHA recommendations for accurate blood pressure measurement. Patients should avoid smoking, caffeine, or exercise within 30 minutes before measurement; empty his or her bladder; then sit quietly in a comfortable chair with back support for at least 10 minutes before measurement and remain still during the measurement. The patient's limb should be supported to measure blood pressure to ensure that the blood pressure cuff is at heart level, using the correct cuff size. Do not take the measurement over clothes. Blood pressure measurements should be performed in the same arm throughout the study. Triplicate blood pressure measurements should be taken approximately 2 minutes apart with a validated, oscillometric upper arm blood pressure

monitor. Trough cuff SBP and DBP values will be assessed based on the pre-defined blood pressure measurement guideline throughout the study. Pulse will be obtained simultaneously with blood pressure measurements;

- Obtain blood sample for clinical laboratory tests (central laboratory; see Appendix B);
- Obtain urine sample for:
 - o Urinalysis (central laboratory; see Appendix B);
 - o Urine pregnancy test for WOCBP only (pre-dose);
 - o UACR; and
 - o 24-hour urine for UACR;
- Obtain serum sample for potassium (local and central laboratories);
- Obtain serum sample for creatinine (central laboratory);
- Obtain plasma sample for PK from all patients (prior to patient's release from the unit);
- Obtain serum sample for aldosterone;

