6.5 Day 112 (Visit 11) End of Study (Safety Follow-Up) ±5 Days

The following procedures will be performed at the End of Study (Safety Follow-Up) Visit (Visit 11):

- Record weight;
- Perform physical examination;
- Perform 12-lead ECG in triplicate (patients should be resting in a supine position for at least 10 minutes prior to assessment);
- Obtain vital signs including pulse rate, respiratory rate, and oral temperature;
- Obtain blood pressure;
 - O Blood pressures are to be obtained according to the AHA recommendations for accurate blood pressure measurement. Patients should avoid smoking, caffeine, or exercise within 30 minutes before measurement; empty his or her bladder; then sit quietly in a comfortable chair with back support for at least 10 minutes before measurement and remain still during

the measurement. The patient's limb should be supported to measure blood pressure to ensure that the blood pressure cuff is at heart level, using the correct cuff size. Do not take the measurement over clothes. Blood pressure measurements should be performed in the same arm throughout the study. Triplicate blood pressure measurements should be taken approximately 2 minutes apart with a validated, oscillometric upper arm blood pressure monitor. Trough cuff SBP and DBP values will be assessed based on the pre-defined blood pressure measurement guideline throughout the study. Pulse will be obtained simultaneously with blood pressure measurements;

- Obtain blood sample for clinical laboratory tests (central laboratory; see Appendix B);
- Obtain urine sample for:
 - o Urinalysis (central laboratory; see Appendix B); and
 - o UACR;
- Obtain plasma sample for PK from all patients;
- Obtain serum sample for pregnancy test (WOCBP only);
- Obtain serum sample for potassium (local and central laboratories);
- Obtain serum sample for creatinine (central laboratory); and
- Record adverse events and concomitant medications.

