8.5 Pregnancy Reporting

If the patient or partner of a patient participating in the study becomes pregnant during the study or within 90 days of discontinuing study drug, the Investigator should report the pregnancy to Worldwide Drug Safety within 24 hours of being notified. Worldwide Drug Safety will then forward the Exposure In Utero form to the Investigator for completion.

A patient becoming pregnant while on study drug will immediately be withdrawn from the study and early termination study procedures will be performed.

The patient or partner should be followed by the Investigator until completion of the pregnancy. If the pregnancy ends for any reason before the anticipated date, the Investigator should notify Worldwide Clinical Safety. At the completion of the pregnancy, the Investigator will document the outcome of the pregnancy. If the outcome of the pregnancy meets the criteria for immediate classification as an SAE (ie, postpartum complication, spontaneous abortion, stillbirth, neonatal death, or congenital anomaly), the Investigator should follow the procedures for reporting an SAE.

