- 12. Blood pressure and heart rate measurements will be obtained every 20 minutes during the interval of 06:00:00 hours to 21:59:59 hours (to coincide with the daytime, awake period), and every 30 minutes during the interval of 22:00:00 hours to 05:59:59 hours (to coincide with the nighttime, sleeping period). During the 24-hour ABPM recording period, a diary will be provided to the patient. Instructions and training will be provided to the site staff, who will in turn provide instructions to the patient.
- 13. If a patient has completed the 24-hour ABPM recording since their last visit, 24-hour ABPM data will be downloaded at the site during the ET Visit.
- 14. Clinical laboratories include chemistry, hematology, coagulation, and urinalysis. See Appendix B for the complete list of clinical laboratory analytes assessed for this study.
- 15. Only clinical chemistry will be conducted at the end of run-in period (Visit 3).
- 16. All patients must have a serum potassium ≤ 4.8 mmol/L at both Screening and the end of the placebo run-in period (Visit 3).
- 17. Serum pregnancy tests will be obtained at Screening, EOS, and ET. A urine pregnancy test will be obtained at pre-dose on Day 1.

- 18. Post-menopausal women only.
- 19. Serum/plasma samples taken during the study will be stored at a central laboratory for determination of various additional biomarkers, including but not limited to galectin-3, N-terminal of the prohormone brain natriuretic peptide, interleukin-6, collagen biomarkers, and C-reactive protein. The panel of biomarkers and time points for analysis will be determined prior to the database lock.
- 20. Plasma samples are to be collected prior to patient's discharge from the unit.
- 21. Plasma samples are to be collected pre-dose. If patients are not dosed in the unit on those days, a PK sample will be collected, and the date and time of the last dose will be recorded.
- 22. Open-label placebo will be dispensed at Visit 2.
- 23. The first dose of the study drug is to be administered.
- 24. The daily dose of the study drug is to be administered.
- 25. If a patient's compliance to medications (including both open-label placebo and current antihypertensive medications) is < 80% or > 120% at Visit 3, he/she will not be eligible for the study and no further visits will be performed.

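### Pregnancy on study drug requires immediate withdrawal, but no pregnancy test is scheduled while the drug is being taken

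*Combined protocol and SAP*

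**What the plan says.** Two sections deal with stopping for pregnancy, and they differ in force.

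- Section 4.3 opens its list of withdrawal reasons with "Participation of a patient in this clinical study may be discontinued for any of the following reasons". Pregnancy is one item, with no timing attached.
- Section 8.5 is unconditional: "A patient becoming pregnant while on study drug will immediately be withdrawn from the study and early termination study procedures will be performed".

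The tests are set out in Appendix A, footnote 17: "Serum pregnancy tests will be obtained at Screening, EOS, and ET. A urine pregnancy test will be obtained at pre-dose on Day 1". The visit lists in Section 6 agree with the footnote. The Day 112 test belongs to the safety follow-up visit, after treatment has ended. Under Section 6.6 the Early Termination visit takes place once study drug has been stopped, and Appendix A footnote 2 limits it to patients who leave the study early.

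Section 4.1, criterion 6, adds that women of childbearing potential "must agree to use 2 medically accepted, effective methods of birth control during the study and for 90 days after the end of the study". It describes adequate contraception as having a failure rate below 1% per year when used consistently and correctly.

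**The concern.** A rule that requires immediate action works best when something in the schedule can set it off. Here every scheduled test falls either before the first dose or after dosing has ended. A woman who conceives early in treatment could take study drug to Day 84 without meeting a scheduled test.

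The protocol itself treats fetal exposure as serious. It asks for two contraceptive methods, continued contraception for 90 days afterwards, reporting within 24 hours of notification, and follow-up to the end of the pregnancy. What is at stake is the length of any exposure on drug. Sample size, type I error and power are not affected.

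**Working it through.** **Step 1: tests against visits.**

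- Screening (Section 6.2): serum test.
- Day 1 (Section 6.4.2): urine test before the first dose.
- Days 7, 14, 28, 42, 56 and 84 (Sections 6.4.3 to 6.4.5, 6.4.7, 6.4.8 and 6.4.10): no test at any of the six clinic visits.
- Days 40 and 82 (ambulatory monitoring visits, Sections 6.4.6 and 6.4.9): no test.
- Day 112 (Section 6.5): serum test.
- Early Termination (Section 6.6): serum test, after drug has stopped.

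The number of scheduled tests between the first dose and the end of dosing is therefore 0.

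**Step 2: the gap for a patient who completes.**

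- Nominal: 112 − 1 = 111 days.
- With the ±5-day window at Day 112: 107 − 1 = 106 to 117 − 1 = 116 days.
- Section 5.1 states: "The duration of the double-blind treatment period will be 84 days". All of those days lie inside the gap, and about 112 − 84 = 28 days off drug follow before the next test.
- Illustration: conception at Day 14 would leave up to 84 − 14 = 70 further dosing days.

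Patients who stop drug but stay in the study are asked to continue visits (Section 5.4 and Table 1). They have no Early Termination visit, so their next scheduled test is also Day 112.

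**Step 3: how many pregnancies to expect.** The protocol does not give the number of women of childbearing potential. Assume 2% to 10% of the 240 planned patients.

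- Women: 0.02 × 240 = 4.8, about 5; 0.10 × 240 = 24.
- On active drug (two of three equal arms): 4.8 × 2/3 = 3.2, about 3; 24 × 2/3 = 16.
- Expected pregnancies over 84 days = women × annual failure rate × 84/365. At 1% per year, the upper limit in criterion 6: 5 × 0.01 × 0.230 = 0.012; 24 × 0.01 × 0.230 = 0.055. That is about 0.01 to 0.06 in the trial.
- On active drug: 3.2 × 0.01 × 0.230 = 0.007; 16 × 0.01 × 0.230 = 0.037. That is about 0.01 to 0.04.
- Sensitivity: at ten times that failure rate (an assumption) and the upper number of women, 24 × 0.10 × 0.230 = 0.55 in the trial.

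**The case against.** The strongest reply is that nothing here conflicts. Footnote 17 and the visit lists match. The reporting duty in Section 8.5 starts when the investigator is notified, and it also covers partners of patients, for whom no test is scheduled. A withdrawal rule can function without a scheduled test behind it. Two methods of contraception are required, so few pregnancies should occur, and how often to test depends partly on reproductive-risk information to which the protocol only refers, in the Investigator's Brochure.

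Most of this stands. A reader might infer that the rule cannot operate, or that detection rests wholly on the patient. The documents support neither reading. Investigators assess adverse events at each visit (Section 8.1), concomitant medications are recorded at every clinic visit, and nothing bars an unscheduled test. The small expected number in the working is also a fair answer to any suggestion that many exposed pregnancies are likely.

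Two things remain. Contraception lowers the risk but does not detect a failure. And the general statement in Appendix B that pregnancy tests will be given to all women of childbearing potential names no visit, so it adds nothing to the on-treatment schedule.

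**Conclusion.** The point holds as a detection gap. The mandatory rule in Section 8.5 has no scheduled test that could trigger it on any of the 84 dosing days, and for a completer the gap between tests is 111 days (106 to 116). Separately, the permissive *may* of Section 4.3 and the mandatory wording of Section 8.5 should be reconciled.

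The day counts come straight from the schedule and need no assumption. The expected number of pregnancies does: it rests on the assumed 2% to 10% share and on the contraceptive failure rate. It is small across the range shown, so the case for change is the low cost of closing the gap rather than the number of events. It would be wrong to call this a contradiction that disables the stopping rule.

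**What to change.** Reconcile Sections 4.3 and 8.5 on whether withdrawal for pregnancy is optional or mandatory, and bring Appendix A footnote 17 and the Section 6.4 visit lists into line, so that the schedule can detect a pregnancy while drug is still being taken. Which wording stands, and whether and at which visits to test, is for the sponsor to decide.

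Urine is already collected at Days 7, 14, 28, 42 and 56 for urinalysis and UACR, and a urine pregnancy test is already a Day 1 procedure. Testing at any of these visits would need no extra visit or sample. Day 84 is not a useful choice for this purpose: unused drug is collected and none is dispensed, so a test there could not shorten exposure. Even if all five earlier visits were used, the last 84 − 56 = 28 dosing days would have no later test on drug.

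The cost is test strips for a small number of women, a few more results to document, and a protocol amendment. Under Section 12.1 the amendment needs IRB/IEC approval, here across approximately 90 sites, so it would sensibly be combined with other changes.
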